7.5.3 Entire Study Termination

The entire study may be suspended or terminated by the Sponsor for safety or other unanticipated reasons or upon request of regulatory agencies. Criteria for premature study termination or suspension are detailed in [Section 14.1, Criteria for Premature Termination or Suspension of the Study](#).

7.5.4 Individual Study Site Termination

Study participation may be suspended or terminated at an individual investigational site for various reasons. Criteria and procedures for premature termination or suspension of an investigational site are detailed in [Section 14.2, Criteria for Premature Termination or Suspension of Investigational Study Sites](#) and [Section 14.3, Procedures for Premature Termination or Suspension of the Study or Investigational Sites](#).

7.5.5 Individual Subject Discontinuation

During this study, it is anticipated that some subjects may permanently discontinue study medication (vadadustat or darbepoetin alfa) for any of the following reasons:

- Unacceptable toxicity or drug intolerance
- Investigator discretion
- Subject withdrawal of consent
- Subject becomes pregnant
- Subject receives kidney transplant
- Lack of efficacy
- Other reasons.

Lack of efficacy is defined as inadequate response to darbepoetin alfa or vadadustat in the Investigator's opinion.

Subjects who undergo a solid organ (including kidney), hematopoietic stem cell, or bone marrow transplantation will have their study medication (vadadustat or darbepoetin alfa) permanently discontinued.

See [Section 9.4, Study Medication Stopping Rules](#) for additional details on the management of subjects with ALT and AST abnormalities.

It is important to continue to follow subjects that permanently discontinue study medication. Please see [Section 7.5.5.1, Temporary Interruption of Study Medication](#) and [Section 7.5.5.2, Permanent Discontinuation of Study Medication](#), and [Appendix A: Schedule of Activities](#).

Receipt of rescue therapy is not a reason for permanent study medication discontinuation. While receiving ESA rescue, subjects must temporarily discontinue study medication (vadadustat or darbepoetin alfa), but should resume study medication once rescue therapy has ended, as detailed in [Section 8.4.7, Rescue Therapy](#).

As part of the informed consent process, only subjects who fully understand and agree to full participation and long-term follow-up should be consented to participate.

7.5.5.1 Temporary Interruption of Study Medication

Subjects who temporarily interrupt study medication (vadadustat or darbepoetin alfa) treatment after the first dose and prior to completion of the study will continue with study visits and assessments. **Unless contraindicated, treatment should be resumed wherever possible and routinely considered at every visit following study medication discontinuation.** If a subject does not return for a scheduled visit, every effort should be made to contact the subject. If a subject's

study medication has been temporarily interrupted for more than 60 days, the Investigator should contact the Medical Monitor before resuming study medication.

7.5.5.2 Permanent Discontinuation of Study Medication

Subjects who permanently discontinue study medication prior to global study completion are expected to continue to be followed post discontinuation of study medication. These subjects are to have their EOT visit at the time of permanent discontinuation of study medication, have the Follow-up visit 4 weeks after the EOT visit and continue to be followed through global study completion. At global study completion, each subject will have an End of Study (EOS) assessment to complete participation in the study. Receipt of rescue therapy is not a reason for permanent study medication discontinuation. While receiving ESA rescue, subjects must temporarily discontinue study medication but should resume study medication following the end of rescue therapy.

For subjects who permanently discontinue study medication, the Investigator will resume standard-of-care treatment, including ESAs and iron therapy, as deemed appropriate.

It is important to continue to follow subjects that permanently discontinue study medication.

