8.5.2 Erythropoiesis-stimulating Agents

For all subjects, it is recommended that no additional ESA doses be administered after Screening visit 2 (SV2) and prior to the Randomization visit. Non-protocol ESAs are prohibited from Randomization until the end of the study, unless the subject is receiving ESA rescue therapy, interrupts study medication for other reasons, or permanently discontinues study medication. Reasons for ESA use will be captured in the appropriate CRF (e.g., adverse event, inadvertent administration, etc.).

Concomitant use of an ESA with study medication is strictly prohibited.

In the setting of ESA rescue therapy, the initial dose of ESA rescue therapy may be administered on the same day as the last vadadustat dose prior to vadadustat dose interruption (see [Section 7.5.5.1, Temporary Interruption of Study Medication](#)) if deemed medically necessary at the discretion of the Investigator. Guidelines for ESA administration as rescue therapy are provided in [Section 8.4.7.2, Erythropoiesis-stimulating Agent Rescue \(Optional\)](#).

All efforts will be made to avoid inadvertent administration of ESAs resulting from following routine ESA hemodialysis protocols (e.g., dialysis center ESA protocols for subjects on hemodialysis). If ESA is inadvertently administered to subjects actively receiving vadadustat treatment, vadadustat treatment will be stopped and the event will be reported as a protocol deviation.

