11.1.1 Sample Size for the Primary Efficacy Endpoint

The primary efficacy endpoint is defined as the mean change from Baseline in Hb (mean pretreatment Hb) to the average Hb over the primary evaluation period (mean Hb from Weeks 24 to 36, inclusive).

The primary efficacy objective of this study is to show that vadadustat is noninferior to darbepoetin alfa within the noninferiority margin. Noninferiority will be established based on a margin of -0.75 g/dL (for vadadustat minus darbepoetin alfa).

For the primary efficacy analysis in this study, it is assumed that the mean change from Baseline in Hb for vadadustat will be the same as for darbepoetin alfa, and the common standard deviation for the mean change from Baseline is assumed to be 1.5 g/dL. Noninferiority will be established based on a 2-sided 95% confidence interval (CI) for the difference between the vadadustat group and darbepoetin alfa and using a noninferiority margin of -0.75g/dL. With these assumptions and approximately 150 subjects per treatment group for the primary efficacy analysis, the noninferiority assessment will have >90% power.

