11.6.1.1 Primary Analysis of Primary Efficacy Endpoint

The primary analysis will use an analysis of covariance (ANCOVA) with multiple imputation, stratified by the randomization strata and using Baseline Hb as the covariate. A 2-sided, 95% confidence interval (CI) will be calculated for the difference between treatment groups (vadadustat minus darbepoetin alfa).

Noninferiority of vadadustat will be established if the lower limit of this CI is ≥ -0.75 g/dL.

The primary analysis will be performed using the randomized population and the assigned treatment as described in [Section 11.2, Study Analysis Populations](#). All data collected during the study for subjects included in the randomized population at the time of analysis, including data collected at any point after the initiation of rescue therapy as well as after early discontinuation of study medication treatment, will be used for the primary analysis. Missing data will be handled using multiple imputation methodology as described in the SAP.

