11.6.1.2 Sensitivity Analyses of Primary Efficacy Endpoint

The following sensitivity analyses will be conducted:

- Primary analysis will be repeated using the full analysis population.
- Primary analysis will be repeated using only subjects with available Hb data during the primary evaluation period, ie, excluding subjects with no available data during the primary evaluation period.
- Primary analysis will be repeated using the PP population with the actual treatment received.
- Primary analysis will be repeated with alternate approaches to imputation of missing data as described in the SAP.
- Primary analysis will be repeated with imputation of data which may have been affected by a subject's having received any form of rescue (transfusion or ESA). Details are provided in the SAP.

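### The rescue sensitivity analysis is triggered only by rescue, so hemoglobin under non-study ESAs given during interruption or after stopping is not addressed in the randomized population

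*Protocol*

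**What the plan says.** All references are to protocol Version 7.0 (Amendment 6).

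Section 8.5.2 prohibits non-protocol ESAs after randomization "unless the subject is receiving ESA rescue therapy, interrupts study medication for other reasons, or permanently discontinues study medication". These are three separate situations. For the last of them, section 7.5.5.2 states that "the Investigator will resume standard-of-care treatment, including ESAs and iron therapy", as deemed appropriate.

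Sections 7.5.5, 7.5.5.2 and 8.4.7.2 describe ESA rescue as a temporary procedure. Study medication is interrupted, the rescue ESA is given, and study medication then resumes. Rescue is not a reason for permanent discontinuation.

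Section 11.6.1.1 says that Hb collected after rescue and "after early discontinuation of study medication treatment, will be used for the primary analysis". Section 11.6.1.2 lists five sensitivity analyses. The one directed at ESA and transfusion effects imputes data that may be affected by a subject's "having received any form of rescue (transfusion or ESA)", with details left to the SAP. Section 11.5 describes the purpose in the same terms, as assessing the effect of rescue therapy.

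**The concern.** The comparator is an ESA. A darbepoetin subject who stops and goes back to an ESA stays within the comparator's class. A vadadustat subject who does the same leaves the test drug for the comparator's class, and any central-laboratory Hb from Weeks 24 to 36 still counts for vadadustat. Lack of efficacy is a listed reason for stopping (7.5.5), so poor responders can be among those who move.

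If vadadustat holds Hb less well than darbepoetin while it is taken, this contamination shrinks the observed difference and makes noninferiority easier to show. A rescue-type sensitivity analysis exists to reveal that. As worded, it removes the contamination from one of the three permitted ESA situations and leaves it from the other two.

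**Working it through.** **Which analyses keep Hb under a non-rescue ESA**

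- Primary (randomized population): kept, by 11.5 and 11.6.1.1.
- Full analysis population: kept. It needs at least one dose and one Hb in the primary evaluation period, and subjects are analyzed as randomized (11.2).
- Available-data analysis: kept. It drops only subjects with no Hb in the period.
- Alternate imputation: concerns missing values, not Hb observed under an ESA.
- Rescue imputation: kept on the wording, because rescue is the trigger.
- Per protocol: partly removed. Section 11.2 requires study medication during Weeks 24 to 36, at least two Hb values in that period, no rescue in the 8 weeks before it, and no deviation affecting the primary endpoint. A subject who stopped before Week 24 and did not resume is therefore out. Two groups can stay in: those who stop within the window and then take an ESA, and those given a non-rescue ESA during an interruption who later resumed. Section 8.5.2 permits both uses, so neither is a deviation in itself.

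**Reproducing the plan's power**

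Inputs from 11.1.1: "Noninferiority will be established based on a margin of -0.75 g/dL (for vadadustat minus darbepoetin alfa"); "the common standard deviation for the mean change from Baseline is assumed to be 1.5 g/dL"; "it is assumed that the mean change from Baseline in Hb for vadadustat will be the same as for darbepoetin alfa"; "approximately 150 subjects per treatment group for the primary efficacy analysis". The interval is a two-sided 95% CI.

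- SE = 1.5 × √(2/150) = 0.173 g/dL
- Power = Φ(0.75/0.173 − 1.96) = Φ(2.37) = 99.1%

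This agrees with the stated power above 90%. The sample size is not in question.

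**Illustration of dilution**

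Let f be the share of the vadadustat arm whose Weeks 24 to 36 Hb is ESA-driven and equal on average to the darbepoetin arm, and let d be the true on-drug deficit. The documents give neither, so both are assumptions.

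- Expected observed deficit = (1 − f) × d
- Chance of meeting the margin = Φ((0.75 − (1 − f) × d)/0.173 − 1.96)

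With d = 0.75 g/dL:

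| f | Expected observed deficit (g/dL) | Chance of meeting margin |
|---|---|---|
| 0% | 0.750 | 2.5% |
| 10% | 0.675 | 6.3% |
| 20% | 0.600 | 13.7% |
| 30% | 0.525 | 25.4% |

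Conversely, the on-drug deficit that would appear as exactly 0.75 g/dL is 0.75/(1 − f): 0.83, 0.94 and 1.07 g/dL for f of 10%, 20% and 30%.

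**The case against.** Four counter-arguments deserve weight.

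**The per-protocol analysis already deals with it.** A reader might infer that every robustness check misses these subjects, or that the main route is left untouched. The documents support neither reading. The requirement for study medication in Weeks 24 to 36 removes those who stopped earlier and did not resume, and nothing in the protocol ranks the three ESA situations by frequency. What remains is the two groups named above. The per-protocol set also selects on behavior after randomization, so it cannot replace an imputation analysis in the randomized population.

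**The SAP may define the trigger broadly.** Section 11.6.1.2 defers to the SAP, which was not available for this review, and it may already count any non-study ESA. But the protocol itself fixes the trigger as rescue and elsewhere treats rescue as distinct from ESA use after stopping. If the SAP reads more widely, only the protocol wording needs aligning.

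**Switched subjects may supply little Hb.** After permanent discontinuation, section 7.5.5.4 makes visits flexible, and its list of optimal data omits Hb. Section 11.5 expects planned visits to continue, so some values will exist. Subjects with none in the period are multiply imputed. This lowers f by an unknown amount.

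**The percentages are not error rates.** This stands. A reader might take 6%, 14% or 25% as an inflated type I error. Under a treatment-policy estimand, however, the true deficit is then 0.675, 0.60 or 0.525 g/dL, which lies inside the margin, so declaring noninferiority is not an error. Subjects who stopped for lack of efficacy may also respond poorly to an ESA, in which case control-like Hb overstates the dilution.

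**Conclusion.** The point holds as a gap in one sensitivity analysis, and it is worth closing. It is not a fault in the primary analysis. On the protocol's wording, Hb under non-study ESAs given during interruption for other reasons or after permanent discontinuation stays in the primary, full-analysis and rescue-imputed results. The per-protocol analysis removes only part of it.

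The direction favors noninferiority if there is a true on-drug deficit. The size cannot be derived from the documents. The tabulated figures rest on an assumed f, control-like Hb in the switched subjects, an on-drug deficit exactly at the margin, and the protocol's SD and sample size. They show only how far an on-drug effect could be diluted.

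**What to change.** In 11.6.1.2, and in the matching SAP text, replace the rescue trigger by: *any RBC transfusion or any non-study ESA for any reason, including during interruption of study medication or after its permanent discontinuation*. Impute Hb affected from that point on. Leave the treatment-policy primary analysis, the other sensitivity analyses and all treatment rules as they are.

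The cost is a wider definition in one planned analysis and more imputed data, hence more reliance on the imputation model. The analysis also needs ESA start dates. The CRF captures reasons for ESA use (8.5.2), and subjects are asked at each study visit about medications started or discontinued (9.2.1). Neither is among the optimal data listed for follow-up after discontinuation (7.5.5.4), so the sponsor should confirm that ESA dates are recorded for those subjects at least through Week 36.

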7.5.5.3 Complete Withdrawal from Further Study Visits/Assessments

A subject has the right to withdraw consent for participation in the study. Withdrawal of consent is a subject's refusal of ALL methods of follow-up noted in the informed consent form: procedures, participation in reduced procedures/study visits, telephone contact only or alternative contact only, source document or designated alternative contact, or access to medical records from alternative sources.

It is important to provide options for the subject to consider for long-term follow-up before the subject withdraws consent. It is important for the Investigator to review options with a subject that would allow follow-up through global study completion before the subject withdraws consent. For subjects considering withdrawal of consent, the Investigator should consult with the Medical Monitor to ensure all options have been explored and that there is complete understanding by the subject for what constitutes withdrawal of consent.

7.5.5.4 Procedures to Support Continued Study Participation

As part of the informed consent process, only subjects who fully understand and agree to full participation and long-term follow-up should be consented to participate. **It is important that subjects understand the long-term duration and purpose of a cardiovascular outcome trial and that the subject (or designee) continue to allow follow-up through global study completion which could be several years, even post subject's permanent discontinuation of study medication.**

In all cases of impending study medication discontinuation or subject request for stopping study visits, the Investigator will discuss with the subject his/her options of continuing in the study. It is important to continue to follow every randomized subject, even if discontinued study medication, through global study completion at a frequency and approach that is agreed to between the Investigator and subject. Visit schedule and assessments are flexible and at the discretion of the Investigator and subject and will be clearly documented in the medical chart.

Optimal data collection would include the following assessments through global study completion:

- EOS subject status (must collect at minimum)
- MACE Endpoint Questionnaire
- AE Assessment

The protocol allows flexibility of follow-up to maintain the subjects in active status post permanent discontinuation of study medication. For those subjects who decline full participation in the study post discontinuation of study medication, other options for continued follow-up on a subject include (but are not limited to):

1. Reduced frequency of on-site visits
2. Telephone visits in lieu of on-site visits
3. Telephone or any contact method (e.g., email, site staff visit subject's home, etc.) to verify vital status
4. Telephone or any contact method with an alternative person (family member or medical designee)
5. Study team access to medical records for reporting MACE data or vital status

In the most extreme case, the protocol will accommodate minimal contact with a subject or alternative method to obtain the subject's vital status. The objective is to **keep a subject's study status active** to ascertain at a minimum vital status (alive or deceased) at the global study completion.

The Investigator will ensure understanding and documentation of the reason(s) for a subject's desire to stop study procedures or stop study medication.

7.5.5.5 Procedures to Prevent “Lost to Follow-up”

The Investigator must make every effort to contact subjects who fail to return for scheduled visits so that they will not be declared “lost to follow-up.” These actions must include, but are not limited to, the following:

1. Contact all numbers for the subject and their listed contacts (to be collected in source at the subject's entry into the study), as applicable. This includes making calls after normal business hours or on holidays and weekends.
2. Contact the subject's primary care physician, referring specialist, pharmacist, and/or other healthcare professional (using the contacts provided by the subject at entry into the study), as applicable.
3. Send email, text, and postal mail with registered (traceable or trackable) letters to all the subject's addresses and contact persons, as applicable. Registered (traceable or trackable) letters will be returned with a copy of the signature from whomever signed, which can be compared to the ICF for vital status data. If undeliverable, then send non-registered standard letters, which may be forwarded to a new address if the subject has moved.
4. Review available medical records/notes for details of hospitalizations, clinic visits, or other procedures that may indicate the status of the subject, as applicable.
5. Utilize the internet to search for additional contact information, as applicable.

6. Check local, regional, and national public records to locate the subject or search for mortality status as allowed by law, as applicable.

It is important to obtain at a minimum vital status (alive or deceased) at the global study completion for all randomized subjects, including those that have been LTFU during the course of the study.

The Sponsor may utilize a third-party provider in accordance with all applicable guidelines and legislation to assist the site in locating contact information for all subjects during the study or in locating the vital status for all of their randomized subjects in anticipation of the global study completion (end of trial).

8 STUDY PRODUCT AND TREATMENT OF SUBJECTS

8.1 Study Product, Supplies, and Storage

Oral vadadustat and darbepoetin alfa for injection will be provided and shipped by the Sponsor or its designated supplier/distributor. Both vadadustat and darbepoetin alfa will be supplied as open-label supplies. All study medication supplies must be kept in a temperature-controlled, locked facility, accessible only to authorized study personnel.

The Investigator or designated study personnel will be responsible for preparing study medication for dispensing to the subject (Section 8.2, Dispensing Procedures) and for study medication supply accountability ([Section 8.3, Product Accountability and Destruction](#)).

8.1.1 Vadadustat

Vadadustat will be provided as 150 mg white to off-white, round, bi-convex film-coated tablets for oral administration. The tablets will be packaged in high-density polyethylene bottles with childresistant- closures, polypropylene liner, and induction seal. Labeling will be in accordance with current Good Manufacturing Practices (GMP) and local regulatory requirements.

Dose levels utilized in this study will include: 150 mg (1 tablet), 300 mg (2 tablets), 450 mg (3 tablets), and 600 mg (4 tablets) per day.

Vadadustat should be stored per the product label. Please consult the Pharmacy Manual for details on storage and managing temperature excursions.

8.1.2 Darbepoetin Alfa

Darbepoetin alfa will be provided in its commercially-approved primary packaging and stored per the US PI for US sites or EU SmPC for non-US sites for adult patients with CKD on dialysis.

8.2 Dispensing Procedures

The Investigator will maintain record of all vadadustat tablets and darbepoetin alfa injections dispensed to and returned from each subject during the study. Subjects will receive either vadadustat tablets or darbepoetin alfa according to the randomization assignments provided via the IWR system (see [Section 8.4.2, Randomization](#)).

